#### OTHER SAFETY ASSESSMENTS

Not applicable.

#### 9.5.2 Schedule of Procedures/Assessments

Table 4 and Table 5 present the schedule of procedures/assessments for the Core Study.

Phase			Treatment								
Period	Pretreatment	retreatment Titration Maintenance Follow- Un a								Early Discontinuation	Unscheduled
Visit	1	2 b	3 b	4 c	5°	6 c,d,e	7°	8 c,f	Ср	Discontinuation	
Week	-2	0	2	4	8	12	14	16	20		
Days	-14	1	15	29	57	85	99	113	141		
Procedures/Assessments											
Demography	Х										
Informed consent/assent	Х										
Inclusion/exclusion criteria	Х	Х									
Medical history	Х										
Epilepsy medical history	Х										
Prior and concomitant medication(s)	Х	Х	Х	Х	Х	Х	Х	Х	Х	Х	Х
Prior and concomitant AED(s)	Х	Х	Х	Х	Х	Х	Х	Х	Х	Х	Х
Neurological examination g	Х							Х	Х	Х	
Physical examination h	Х							Х	Х	Х	
Vitals and weight	Х	Х	Х	Х	Х	Х	Х	Х	Х	Х	Х
Height/length h	Х	Х						Х		Х	
Head circumference	Х	Х						Х		Х	
Adverse events	Х	Х	Х	Х	Х	Х	Х	Х	Х	Х	Х
Dispense study drug		Х	Х	Х	Х	Х	Х	Xi			Xj
Retrieve unused study drug			Х	Х	Х	Х	Х	Х		Х	Xj
Study drug compliance			Х	Х	Х	Х	Х	Х		Х	Х
Dispense subject's diary	X k	Х	Х	Х	Х	Х	Х	Х		Х	$X^1$
Retrieve and review subject diary		Х	Х	Х	Х	Х	Х	Х	Х	Х	$X^1$
Clinical laboratory tests m, n	Х					Х		Х	Х	Х	Xº
Thyroid function (TSH, fT3, fT4) and IGF-1 tests	Х							Х		Х	
12-lead ECG p	Х			Х		Х		Х	Х	Х	Xq
Perampanel PK blood sampling r					Х		Х	X		Х	X 
Telephone call s		Х	Х	Х	Х	X	Х	X	Х		
CGI-C, CGI-S t		Х						X		X	
Disposition	Х	Χ						X		Х	

#### Table 4Schedule of Procedures/Assessments in Study E2007-G000-238: Core Study – Non-EIAED Subjects

#### Table 4Schedule of Procedures/Assessments in Study E2007-G000-238: Core Study – Non-EIAED Subjects

Phase						Treatn					
Period	Pretreatment	'retreatment Titration						Maintenance		Early Discontinuation	Unscheduled
Visit	1	2 b	3 b	4 c	5°	6 c,d,e	7°	8 c,f			
Week	-2	0	2	4	8	12	14	16	20		
Days	-14	1	15	29	57	85	99	113	141		
Procedures/Assessments											

AE = Adverse event, AED = Anti-epileptic drug, CGI-C = Clinical Global Impression of Change, CGI-S = Clinical Global Impression of Severity, CLIA = Clinical Laboratory Improvement Amendments, CRF = case report form, EAP = extended access program, ECG = electrocardiogram, EOT = end of treatment, fT3 = free triiodothyronine, fT4 = free thyroxine, IGF-1 = insulin-like growth factor-1, PK = pharmacokinetics, SAE = serious adverse event, TSH = thyroid-stimulating hormone.

a: To be done within ±6 days of the scheduled visit. Visit applies only to those subjects who complete the Treatment Phase but do not roll-over into the Extension Phase and those subjects who discontinue the study early for any reason after Visit 2 and before Visit 8.

- b: To be done within  $\pm 2$  days of the scheduled visit.
- c: Visits should be done within ± 3 days of the scheduled visit. There must be at least 10 days of treatment between Visits 3 and 4, 4 and 5, and 5 and 6.
- d: Upon successful completion of Visit 6, subjects will begin the Maintenance Period of the study.
- e: No dose titration is allowed at this visit or future visits.
- f: Visit 8 will be considered the first visit of the Extension Phase for subjects who choose to continue into the Extension Phase.

g: For clinic visits other than those specified, physical and complete neurological exams, including evaluation of the cranial nerves, motor, sensory, brainstem, cerebellar, and autonomic functions, will only be performed when there is a complaint from the parent/guardian.

- h: Two measurements of height/length should be taken. Each measurement should be recorded as a separate entry on the Vital Sign CRF.
- i: Only for those subjects who roll-over into the Extension Phase.
- j: Unused study drug to be retrieved and study drug dispensed only for subject requiring dose increases at Unscheduled Visits.
- k: To include the number and type of seizures for the 4 weeks before the Pretreatment Phase.

1: As needed.

- m: Lipid and blood glucose tests to be conducted under fasting conditions, whenever practically feasible. (revised per Amendment 02)
- n: All clinical laboratory tests are to be performed at the central laboratory. At Screening/Baseline (Visit 1), use of local laboratory test results (hematology, clinical chemistry, thyroid function and IGF-1 test) may be allowed if the subject's local laboratory tests are obtained from a CLIA-certified laboratory within 4 weeks before Visit 1. In these cases, to enable safety evaluation (eg, to assess whether there are treatment-emergent shifts in laboratory values from baseline), all post-baseline labs must be conducted at the same local laboratory using same assays as those used at Screening/Baseline. (revised per Amendment 02)
- o: During the unscheduled visits, clinical laboratory tests will only be done if an abnormality was noted at the previous visit or per the discretion of the investigator. (revised per Amendment 02)
- p: If the subject has a normal ECG baseline reading, but during any visit thereafter if there is any clinically significant ECG abnormality (as determined by the investigator), 3 consecutive ECGs separated by 5 to 10 minutes will be performed at that visit to confirm the abnormality.
- q: During the unscheduled visits, ECG will only be done if the results from the previous visit were deemed to be clinically significant by the investigator.
- r: Blood samples (1.0 mL each) will be collected from all subjects for the determination of perampanel concentrations. The date and time of PK sample collection will be recorded on the CRF, as well as the date and time of the last 3 perampanel doses administered before the PK sample collection. Subjects aged 1 to less than 24 months will have 1 PK sample taken at anytime after the last perampanel dose per PK visit. Subjects aged 2 to less than 4 years will have 2 PK samples taken (1 predose and 1 postdose between 1 and 5 hours after dose administration) per PK visit. See Section 9.5.1.4 for details. After centrifugation, plasma sample harvested will be aliquoted onto 2 Microtainer tubes (1 primary and 1 back-up sample). (revised per Amendment 02)

			-						-		
Phase						Treatn					
Period	Pretreatment		Titration			Maintenance Follow- Up a			Early Discontinuation	Unscheduled	
Visit	1	2 b	3 b	4 c	5°	6 c,d,e	7°	8c,f			l
Week	-2	0	2	4	8	12	14	16	20		
Days	-14	1	15	29	57	85	99	113	141		
Procedures/Assessments											1

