- *Follow-Up Period:* Subjects will not receive study drug during this period. Subjects who do not continue into the Extension Phase after completing the Maintenance Period, or those who discontinue early from the study will be required to complete the Follow-up Period after their last dose in the Treatment Phase. Subjects who switch to commercially available perampanel or who enter into EAP upon completion of study treatment need not to undergo Follow-up Visit; however, sites will conduct a telephone contact 28 (+6) days after the last dose of study drug to follow adverse events (AEs) and report any serious adverse events (SAEs) that occur within 28 days of the last study drug administration. (revised per Amendment 02)

After every 4th subject in the age group 1 to less than 24 months completes the Maintenance Period, an interim analysis (safety, tolerability, and PK) will be conducted whereby dose-normalized exposure will be compared to that observed in other studies in subjects between  $\geq 2$  and <18 years of age. If the exposure of the subjects is significantly different from that observed in subjects ages  $\geq 2$  to <12 years from other clinical studies or that are predicted from PK modeling and simulation, or if non-linear PK is observed, the sample size will be increased to at least 24 subjects with evaluable PK data, and the target dose or dosing regimen of those subjects may be modified via protocol amendment, depending on the PK of the previous subjects. PK data collected in older age cohort (2 to less than 4 years) will also be examined in the interim PK analyses. (revised per Amendment 02)

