#### **Other Dosing Considerations**

Down-titration of perampanel upon early discontinuation or completion of the study is not necessary, because the plasma half-life of perampanel is between  $\sim 25$  (in the presence of EIAED) to 105 (in the absence of EIAED) hours. As such, plasma concentrations decrease gradually following stopping perampanel. If, in the clinical judgment of the investigator, down-titration of perampanel is still deemed necessary, the investigator must discuss the down-titration before the early discontinuation with the Medical Monitor.

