#### Adverse Events and Events Associated With Special Situations

An AE is any untoward medical occurrence in a patient or clinical investigation subject administered an investigational product. An AE does not necessarily have a causal relationship with the medicinal product. For this study, the study drug is perampanel (E2007).

The criteria for identifying AEs in this study are:

- Any unfavorable and unintended sign (including an abnormal laboratory finding), symptom, or disease temporally associated with the use of an investigational product, whether or not considered related to the investigational product (Note: Every sign or symptom should not be listed as a separate AE if the applicable disease [diagnosis] is being reported as an AE)
- Any new disease or exacerbation of an existing disease
- Any deterioration in nonprotocol-required measurements of a laboratory value or other clinical test (eg, ECG or x-ray) that results in symptoms, a change in treatment, or discontinuation of study drug
- Recurrence of an intermittent medical condition (eg, headache) not present pretreatment (Baseline)
- An abnormal laboratory test result should be considered an AE if the identified laboratory abnormality leads to any type of intervention, withdrawal of study drug, or withholding of study drug, whether prescribed in the protocol or not

All AEs observed during the study will be reported on the CRF. All AEs, regardless of relationship to study drug or procedure, should be collected beginning from the time the subject signs the study ICF through the last visit and for 28 days following study drug discontinuation. Subjects who fail screening primarily due to AE(s) must have the AE(s) leading to screen failure reported on the Screening Disposition CRF. SAEs will be collected for 28 days after the last dose.

Abnormal laboratory values should not be listed as separate AEs if they are considered to be part of the clinical syndrome that is being reported as an AE. It is the responsibility of the investigator to review all laboratory findings in all subjects and determine if they constitute an AE. Medical and scientific judgment should be exercised in deciding whether an isolated laboratory abnormality should be classified as an AE. Any laboratory abnormality considered to constitute an AE should be reported on the Adverse Event CRF.

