#### 9.5.4.1 Reporting of Serious Adverse Events

All SERIOUS ADVERSE EVENTS, regardless of their relationship to study treatment, must be reported on a completed SAE form by email or fax as soon as possible but no later than 24 hours from when the investigator becomes aware of the event.

Serious adverse events, regardless of causality assessment, must be collected through the last visit (through the last visit in the Treatment Phase and for 28 days after the subject's last dose). All SAEs must be followed to resolution or, if resolution is unlikely, to stabilization. Any SAE judged by the investigator to be related to the study treatment or any protocol-required procedure should be reported to the sponsor regardless of the length of time that has passed since study completion.

Detailed contact information for reporting of SAEs is provided in the Investigator Study File.

For urgent safety issues, please ensure all appropriate medical care is administered to the subject and contact the appropriate study team member listed in the Investigator Study File.

It is very important that the SAE report form be filled out as completely as possible at the time of the initial report. This includes the investigator's assessment of causality.

Any follow-up information received on SAEs should be forwarded within 24 hours of its receipt. If the follow-up information changes the investigator's assessment of causality, this should also be noted on the follow-up SAE form.

Preliminary SAE reports should be followed as soon as possible by detailed descriptions including copies of hospital case reports, autopsy reports, and other documents requested by the sponsor.

The investigator must notify his/her IRB/IEC of the occurrence of the SAE in writing, if required by their institution. A copy of this communication must be forwarded to the sponsor to be filed in the sponsor's Trial Master File.

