# Table 6Schedule of Procedures/Assessments in Study E2007-G000-238:Extension Phase –
Non-EIAED Subjects

Phase	Extension a					
Period		Maintenanc	e			
Visit	9	10	11		Early Discontinuation	Unscheduled
Week	28	40	52	56		
Days	197	281	365	393		
Procedures/Assessments						
Concomitant medications	Х	X	Х	Х	Х	Х
Concomitant AEDs	Х	Х	Х	Х	Х	Х
Adverse events	Х	Х	Х	X	Х	Х
Study drug compliance	Х	Х	Х		Х	Х
Dispense study drug	Х	Х				Xc
Retrieve unused study drug	Х	Х	Х		Х	Xc
Dispense subject's diary	Х	Х	Х		Х	X d
Retrieve and review subject diary	Х	X	X	Х	Х	X d
Physical examination e	Х		X		Х	
Neurological examination e	Х		Х		Х	
Vitals and weight	Х	Х	Х		Х	Х
Height/length f	Х		Х		Х	
Head circumference	Х		Х		Х	
Clinical laboratory tests g	Х	Х	X h	Х	X h	X i
Thyroid function (TSH, fT3, fT4) and IGF-1 tests	Х		Х		Х	
12-lead ECG j	Х		Х		Х	$X^k$
CGI-C			Х		Х	
Telephone call 	Х	X	Х			
Disposition			X		Х	

AE = Adverse event, AED = Anti-epileptic drug, CGI-C = Clinical Global Impression of Change, CRF = case report form, EAP = extended access program, ECG = electrocardiogram, EOT = End of Treatment, fT3 = free triiodothyronine, fT4 = free thyroxine, IGF-1 = insulin-like growth factor-1, SAE = serious adverse event, TSH = thyroid-stimulating hormone.

- a: All visits to be done within  $\pm 6$  days of the schedule.
- b: The Follow-up Visit (4 weeks ± 6 days after the last dose of study medication) applies to those subjects who complete the entire study and those who discontinue early during the Extension Phase. Subjects who switch to commercially available perampanel or who enter into EAP upon completion of study treatment will not need to undergo Follow-up Visit; however, sites will conduct a telephone contact 28 (+6) days after the last dose of study drug to follow AEs and report any SAEs that occur within 28 days of the last study drug administration. (revised per Amendment 02)
- c: Unused study drug to be retrieved and study drug dispensed only for subjects requiring dose increases at Unscheduled Visits.
- d: As needed.

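### The off-drug Follow-up Visit may fall as early as day 22, before the 28-day adverse event collection period ends, and the tables and text time it from different anchors (minor)

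*Protocol*

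**What the plan says.** **Collection period.** Protocol Section 9.5.1.5 has all adverse events collected "through the last visit and for 28 days following study drug discontinuation" and followed for 28 days after the last dose or until resolution, whichever is first. Section 9.5.4.1 has serious events collected "for 28 days after the subject's last dose".

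**Children who stop the drug.** They return for a Follow-up Visit. Sections 9.3.3 and 9.5.5 (subjects who discontinue) time it at 4 weeks ±6 days from the last dose. The Extension tables agree: "The Follow-up Visit (4 weeks ± 6 days after the last dose of study medication" (Table 6 footnote b, and the same in Table 7). The Core tables differ. Footnote a of Table 4 reads "To be done within ±6 days of the scheduled visit", Table 5 has the same rule, and both apply it to completers and to early discontinuers.

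**Other off-drug contact for these children.** The telephone footnotes (s in Tables 4 and 5, the last footnote in Tables 6 and 7) describe one call, at about the midpoint before the Follow-up Visit. They describe none after it.

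**Children who switch to commercial perampanel or enter the extended access program.** They have no Follow-up Visit. Instead, "sites will conduct a telephone contact 28 (+6) days after the last dose of study drug".

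**The concern.** The protocol sets a 28-day period but schedules its closing contact with a window that opens before day 28. If the visit is early, no planned contact asks about the remaining days. The one-sided window that would avoid this is already in the protocol, but only for children who stay on perampanel. The children coming off the drug have the weaker assurance, and no reason is given for the difference.

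Treatment-emergent and serious adverse events are a secondary endpoint, and SAP Section 5.6.2 tabulates treatment-emergent events by onset period, including Follow-up. The study plans 16 to 24 infants and 1 to 26 older children, so a few unascertained days in a few children could alter a small count. Section 9.1 also ends the study at the last subject's last visit, which could formally precede the end of that child's 28 days.

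Separately, two anchors are given for the same visit. Footnote a of Tables 4 and 5 covers early discontinuers, whom Section 9.5.5 times from the last dose.

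**Working it through.** This is calendar arithmetic on the schedule.

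**Inputs**
- Table 4 days: "Days -14 1 15 29 57 85 99 113 141". The last Maintenance visit is Day 113 and Follow-up is Day 141.
- Table 5: last Maintenance visit Day 141, Follow-up Day 169.
- Tables 6 and 7: last Maintenance visit Day 365, Follow-up Day 393.
- Follow-up window: ±6 days in all four tables.
- Window for the last Core treatment visit (footnote c): "Visits should be done within ± 3 days of the scheduled visit".
- Collection period: 28 days after the last dose.

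**1. Reproduce the nominal gap**
- Table 4: 141 − 113 = 28 days
- Table 5: 169 − 141 = 28 days
- Tables 6 and 7: 393 − 365 = 28 days

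The nominal schedule matches the collection period. The gap arises only from the window and the anchor.

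**2. Window timed from the last dose (Sections 9.3.3 and 9.5.5, Tables 6 and 7 footnote b)**
- Earliest: 28 − 6 = 22 days. Latest: 28 + 6 = 34 days.
- Days left after the earliest visit: 28 − 22 = 6, and 6/28 = 21%.

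**3. Window timed from the scheduled visit (Tables 4 and 5 footnote a, Core Study only)**
- Final treatment visit on its nominal day: (141 − 6) − 113 = 22 days.
- Final visit 3 days late, Table 4: (141 − 6) − (113 + 3) = 19 days.
- Final visit 3 days late, Table 5: (169 − 6) − (141 + 3) = 19 days.
- If the last dose was the evening before that late visit: 20 days.
- Days left: 28 − 19 = 9 (9/28 = 32%), or 28 − 20 = 8 (8/28 = 29%).

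Whether 19 or 20 applies depends on age. Under Section 9.5.1.4, children of 2 to less than 4 years are dosed on site at the last Maintenance visit, which gives 19. Children under 24 months dose in the evening, and drug is dispensed at that visit only to those who roll over, so their last dose is ordinarily the evening before. That gives 20.

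**4. Switch or extended-access call**
- 28 to 28 + 6 = 34 days. It is never before day 28, so no days are left over.

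**5. Does changing the sign of the window suffice?**
- A +6-only window on the Table 4 calendar anchor, after a final visit 3 days late: 141 − 116 = 25 days. The gap shrinks but remains, so the anchor must change too.

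**The case against.** Several counter-arguments stand and limit the point.

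- **The duty to collect outlasts an early visit.** Sections 9.5.1.5 and 9.5.4.1 still require 28 days, and related serious events are reportable at any time. A reader might infer that late events would be found only if a parent volunteers them. The text does not go that far: sites remain obliged to collect, and what is missing is a specified contact at which to do so.
- **A reader might take 19 days as the general minimum.** It is a Core-only corner case. It needs a completer who neither rolls over nor switches, a final visit 3 days late, a Follow-up Visit 6 days early, and footnote a read literally against Section 9.1.2.3, which places the Follow-up Period after the last dose. Reading footnote a of Tables 6 and 7 (±6 days on all visits) in the same way would give (393 − 6) − (365 + 6) = 16 days, but footnote b there times this visit from the last dose.
- **Children who stop the drug are not followed less overall.** Core children have a midpoint call and a clinic visit with examinations, laboratory tests and an ECG, and the visit may be as late as day 34. Only the guaranteed end date is earlier than for switchers.
- **A later contact is not wholly excluded in Table 4.** Its telephone row, as extracted, has an X under Follow-up, while Table 5 has none. Footnote s describes no call after the visit, so the mark may be the switch or extended-access call, or a displaced cell. It does not establish a later contact but should be explained.
- **A reader might argue from residual drug.** The documents do not support a general argument. Section 9.4.1 gives a half-life from about 25 hours with an enzyme inducer to 105 hours without, so the longer figure does not apply to Table 5 subjects. No infant volume of distribution is given from which to derive an infant half-life.
- **A reader might dismiss the ±6 days as a shelf-life rule that is irrelevant at a visit without dispensing.** The revision history cites shelf life only for the change from ±7 to ±6, not for having a two-sided window.

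**Conclusion.** The inconsistency holds and is minor. Where the visit is timed from the last dose, it may occur on day 22, leaving up to 6 of 28 days (21%) without scheduled ascertainment. This needs no unusual combination and can occur in both phases. In the Core Study, the calendar anchor can stretch this to 8 or 9 days, but only in the corner case described.

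These are limits on what the schedule permits, not estimates of what will happen. Visits may equally fall on or after day 28, and the documents give no basis for estimating how many children would be seen early. The conclusion assumes that the X in Table 4 is not a call after the Follow-up Visit. No 28-day incidence endpoint is defined and no formal test is planned. The consequence is therefore possible under-ascertainment in a descriptive table of Follow-up-onset events, not a threat to the primary pharmacokinetic objective.

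**What to change.** 1. **Use one anchor.** In Tables 4 to 7 and Sections 9.3.3 and 9.5.5, time the Follow-up Visit from the last dose, and remove the scheduled-visit anchor from footnote a of Tables 4 and 5.
2. **Cover the 28 days**, in one of two ways:
   - set the visit at 28 (+6) days after the last dose, the window already used for the switch and extended-access call; or
   - keep ±6 days and add a telephone contact at day 28 whenever the visit falls before day 28.
3. **Clarify the X** under Follow-up in Table 4's telephone row, and make Table 5 consistent with it.

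The first option under item 2 adds no visit or procedure but cuts the permitted range from 13 calendar days (days 22 to 34) to 7 (days 28 to 34). The second keeps the flexibility and costs one short call for children seen early. The rest is footnote and text wording.

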#### Table 4Schedule of Procedures/Assessments in Study E2007-G000-238: Core Study – Non-EIAED Subjects

S: Telephone interviews with the parent/guardian will be conducted approximately 1 week after Visit 2 and 3, and approximately at the midpoint between each subsequent visit, to ensure that subjects are completing their seizure diaries regularly and to assess AEs, study drug compliance, and concomitant medications, including AEDs. Subjects whose dose was decreased before the scheduled telephone interview will strongly be encouraged to return to the clinic (instead of the scheduled telephone interview) for further consultation with regard to study drug administration. Subjects will then return for their regularly scheduled visit. Subjects not continuing into the Extension phase will have a telephone interview at approximately the midpoint between Visit 8 and the Follow-up Visit after finishing the Maintenance Period when drug has been stopped. Subjects that discontinue the study at any time will have a telephone interview at approximately the midpoint between the EOT Visit and the Follow-up Visit. For subjects who will not need to undergo Follow-up Visit (eg, when switching to commercially available Fycompa or entering EAP after the last study drug administration) will have a telephone interview 28 (+6) days after the last study drug administration. AEs/SAEs that occurred within 28 days after the last study drug administration will be reported. (revised per Amendment 02)

t: CGI-S to be administered at Visit 2, CGI-C to be administered at Visit 8 or early discontinuation.

Phase			Treatment									
	Pretreatment									Follow-		
Period		h	- 1	Ti	tratio	n	L = . 4 .	Mair	itenance	Up a	Early	
Visit	1	2 b	30	4 c	5°	6°	7 c,a,e	8°	9 c,1		Discontinuation	Unscheduled
Week	-2	0	2	4	8	12	16	18	20	24		
Days Days	-14	1	15	29	57	05	115	127	141	109		
Demography	x											
Informed consent/assent	X											
Inclusion/exclusion criteria	X	x										
Medical history	X											
Epilepsy medical history	X											
Prior and concomitant medication(s)	Х	Х	Х	Х	Х	Х	Х	Х	X	Х	Х	Х
Prior and concomitant AED(s)	Х	Х	Х	Х	Х	Х	Х	Х	Х	Х	Х	Х
Neurological examination g	Х								X	Х	Х	
Physical examination h	Х								X	Х	Х	
Vitals and weight	Х	Х	Х	Х	Х	Х	Х	Х	Х	Х	Х	Х
Height/length h	Х	Х							Х		Х	
Head circumference	Х	Х							Х		Х	
Adverse events	Х	Х	Х	Х	Х	Х	Х	Х	Х	Х	Х	Х
Dispense study drug		Х	Х	Х	Х	Х	Х	Х	Xi			$\mathbf{X}^{\mathrm{j}}$
Retrieve unused study drug			Х	Х	Х	Х	Х	Х	Х		Х	$\mathbf{X}^{\mathrm{j}}$
Study drug compliance			Х	Х	Х	Х	Х	Х	Х		Х	Х
Dispense subject's diary	$X^k$	Х	Х	Х	Х	Х	Х	Х	Х		Х	$X^{l}$
Retrieve and review subject diary		Х	Х	Х	Х	Х	Х	Х	Х	Х	Х	$X^{l}$
Clinical laboratory tests m,n	Х					Х	Х		Х	Х	Х	Xº
Thyroid function (TSH, fT3, fT4) and IGF-1 tests	Х								Х		Х	
12-lead ECG p	Х			Х		Х	Х		Х	Х	Х	$X^{p,q}$
Perampanel PK blood sampling r						Х		Х	Х		Х	Xº
Telephone call s		Х	Х	Х	Х	Х	Х	Х	X			
CGI-C, CGI-S t		Х							X		X	

